d) Subject payment (also see below, section 18): For subjects participating in the "Within-Subject" test sessions, payment will be divided in the following schedule: on completion of screening day: \$30; on completion of first TEST SESSION day: \$100; On completion of second TEST SESSION day: \$130. This payment schedule provides appropriate incentive for the subjects to return for the second test day. This is to ensure that subjects return for the second and third test days. If subjects fail screening criteria for recreational drug use prior to any TEST SESSION day, they will not be tested further and will not be paid for that test day. We will recommend that subjects remain in our laboratory for monitoring until six and one half hours after pill ingestion. Should they choose to leave our facility for any reason prior to that time, it will be at their own risk. Their involvement in the study will be completed and payment on the Test Session day will be prorated to \$16 per hour.

e) Venopuncture: Venopuncture for COMT allelic testing in some subjects will occur during the initial visit, before or after what normally is titled the SCREENING SESSION in the studies listed below. A single venopuncture performed by certified individuals within the UCSD Medical Center GCRC/CTRI or Blood Drawing Station will be used to 10 cc of blood for COMT allelic testing. Based on specific needs of the experimental design (e.g. equal number of Met/Met, Val/Met and Val/Val allelic carriers, or subgroups of "high" vs. "low" PPI levels, based on the upper vs. lower quartile of a normal population distribution), subjects may be asked to come back for further testing, if they indicate they would like to do so. If participants continue to the remainder of the study, there will be 2 test days, one of which will involve placebo, and the other day involving an active dose of amphetamine (20 mg), memantine (20 mg) or other approved test drug/dose. The TEST SESSIONS will mimic those in the WITHIN-SUBJECT model below; however, venopuncture occurs only during the first visit.

f) Clinical assessment: Specific clinical assessment tools used in control and schizophrenia subjects are described in Section 10.

g) Test schedules:

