1. The "WITHIN-SUBJECT" study involves a single drug. There will be 2 test days – on the additional test day, subjects will receive either placebo or an active dose of one of the following: amphetamine (20 mg), memantine (10 mg) and memantine (20 mg). Some studies may require a venopuncture for genetic analysis as discussed above. A "model" example of a WITHIN-SUBJECT test schedule is shown below:

Test Day 1

0815-0845 Subject signs required forms, provides urine sample, eats standardized breakfast, venopuncture (if required)

0845-0900 Vital signs (VS) check, hearing and vision test, symptom rating scale.

0900-0915 drug or placebo administration.

0915-0930 VS check; symptom rating scales.

0930-0945 EMG electrodes applied.

0945-1000 VS check; symptom rating scales.

1000-1125 Startle response measurement, including PPI, habituation and intensity assessment.
1125-1140 VS check; symptom rating scales.
1140-1155 Visual LI or Visuospatial priming or MCCB
1155-1210 VS check; symptom rating scales.
1210-1300 Subject offered lunch from cafeteria.
1300-1600 VS check hourly; subject dismissed if VS within established parameters at 1600.

Test Day 2: 7-30 days after Test Day 1

0815-0845 Subject signs required forms, provides urine sample, eats standardized breakfast, venopuncture (if required)
0845-0900 Vital signs (VS) check, hearing and vision test, symptom rating scale.

0900-0915 drug mg or placebo administration: WHICHEVER DOSE WAS NOT RECEIVED ON TEST DAY 1

0915-0930 VS check; symptom rating scales.
0930-0945 EMG electrodes applied.
0945-1000 VS check; symptom rating scales.
1000-1125 Startle response measurement, including PPI, habituation and intensity assessment.
1125-1140 VS check; symptom rating scales.
1140-1155 Visual LI or Visuospatial priming or MCCB
1155-1210 VS check; symptom rating scales.
1210-1300 Subject offered lunch from cafeteria.
1300-1600 VS check hourly; subject dismissed if VS within established parameters at 1600.

Subjects will be instructed to not eat on the morning of the test, and instead will be served a standardized meal 30 min prior to drug administration, so as to maintain a controlled and consistent impact on drug absorption.

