Recruitment of female subjects: As per NIH guidelines, it is important to establish whether observed drug effects on these psychophysiological measures are sex-specific. Our current NIMH application thus proposes the use of female subjects in within-subject studies of drug effects on PPI, LI and related measures. At present, approval for studies in females is sought only for studies with amphetamine and memantine. Methods for these studies will be identical to those described above for male subjects, with the following exceptions: 1) urine pregnancy tests ("Surecheck Early Pregnancy Test") will be completed at the time of initial screening and test day 2 (exclusion: positive test); 2) testing will occur only during post-menses days 1-10; 3) blood will be drawn on the morning of testing and stored for possible later hormonal analyses using the GCRC/CTRI laboratory services; a total of 5 cc will be collected by venopuncture using GCRC/CTRI or hospital phlebotomy services.

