For the drug evaluation study, the proposed drugs carry a very small risk of toxicity or adverse side effects in the doses to be used in this study. The most common side effects associated with each drug are listed in Section 8 above, and typically include nausea, somnolence and dizziness. We do not plan to administer these drugs to subjects in whom it is contraindicated, such as subjects with known cardiovascular or neurological disorders. The doses selected for use in these studies are in the low- or below-therapeutic range for these drugs when they are used clinically, and in most cases, the selected dose is equal to or less than the lowest recommended starting clinical dose for the drug. To address the potential for some of these drugs to produce changes in blood pressure, we will carefully monitor subjects' vital signs, and will not release subjects from the hospital until their vital signs are within normal limits. To address the possible side effect of somnolence, we will instruct subjects to arrange for their transportation from the hospital on test days. For studies that include women of childbearing potential, there is the possibility of unforeseen harm to an unborn child due to the administration of drugs. To address this risk, all female subjects will be asked to provide a urine sample to test for pregnancy and we will exclude participants who test positive. Additionally, all female subjects in these studies will be required to use a non-drug birth control method, such as abstinence, diaphragm, non-hormone intrauterine device to prevent pregnancy during the study. Subjects will be told to report if their menstrual cycle is inconsistent or if suspect that they are pregnant. Drugs will be dispensed by a licensed physician, and a licensed physician will be present on the premises at all times during testing. The consent forms include the related risks specific to the drug it refers to.

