15. RISK MANAGEMENT PROCEDURES AND ADEQUACY OF RESOURCES

The overall risks of this proposal are small. Protection of subject confidentiality and privacy will be rigorously guarded by the assignment of coded numbers to each file in the computer analysis and database. Resulting data will not be released to any subject, and released only to a patient's primary physician when an appropriate release form is signed by the patient. The UCSD psychophysiology research laboratory of [name] has studied over 1000 control subjects and patients without any problems with confidentiality.

For the drug evaluation study, risk management procedures include: 1) Subjects will be asked to refrain from alcohol or other drug use while on the study. 2) Each subject will receive a complete history and physical examination prior to acceptance into the study. 3) A battery of psychological tests will be administered, as will an EKG and urine toxicology screen (which will also be used to test for pregnancy in drug studies including women of childbearing potential). 4) Subjects involved in studies with drugs will arrange for their transportation from the hospital, and any subject reporting any sedation upon completion of the study will be instructed to not operate a motor vehicle until the sedation is resolved. Subjects known or determined to have cardiovascular disease by EKG or patient history will be excluded. All subject information will be kept in a secure and locked area of the laboratory, CTF Building, UCSD Medical Center. Confidentiality will be protected to the extent provided by law.

If a participant has any questions regarding the study, they may contact the PI, [name]., Ph.D., Monday-Friday, 8 a.m. – 4:30 p.m. at [contact]. He may be reached after hours by contacting the UCSD operator at [contact] and having them page [name]. If any emergencies arise related to participating in these studies, the participant may proceed to the nearest emergency room or call 9-1-1.

Subjects will be told that they can terminate the experiment at any time if an aspect of the procedure causes them discomfort.

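### Pregnancy tests are listed at screening and test day 2 only, although active drug can be given on test day 1

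*Protocol*

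**What the plan says.** Section 11 of the protocol lists the ways in which studies in women differ from those in men. The first is that urine pregnancy tests "will be completed at the time of initial screening and test day 2", with a positive result excluding the woman. The same list confines testing to days 1 to 10 after menses.

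The model schedule in section 9.g has, on Test Day 1, "0900-0915 drug or placebo administration". On Test Day 2 the subject gets "WHICHEVER DOSE WAS NOT RECEIVED ON TEST DAY 1", and that day falls "7-30 days after Test Day 1". Urine is collected between 0815 and 0845 on both days, but the schedule does not say what it is tested for.

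Other sections mention pregnancy testing without tying it to a day:

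- Section 14 says women will give urine for a pregnancy test and be excluded if positive. It adds that "all female subjects in these studies will be required to use a non-drug birth control method" and that they should report irregular periods or a suspected pregnancy.
- Section 15 refers to a urine toxicology screen "which will also be used to test for pregnancy in drug studies including women of childbearing potential".
- Section 9.i describes the dip-stick method only.

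**The concern.** A pregnancy test can prevent fetal exposure only if it comes before the active dose. As listed, the tests protect women by treatment order. A woman given placebo first is tested on the day she takes active drug. A woman given active drug first is not; her day-2 test precedes placebo and can only reveal an exposure that has already happened.

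Section 14 names fetal harm as a risk of these studies and offers the urine test as a safeguard. Staff who follow section 11 literally would not run the test on a day when active drug may be given. This is a participant-safety point and does not touch the trial's inference.

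**Working it through.** The protocol gives no figure to reproduce. The check sets the testing rule beside the dosing schedule.

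**1. Coverage of dosing days (sections 11 and 9.g).**

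| Occasion | Pregnancy test listed? | Active drug possible? |
|---|---|---|
| Initial screening | Yes | No |
| Test Day 1 | No | Yes |
| Test Day 2, 7 to 30 days later | Yes | Yes |

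There are 2 dosing days and 1 has a listed same-day test, so 2 − 1 = 1 is uncovered.

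**2. How often day 1 is the active day.** Section 8 states a balanced order for the ongoing memantine study in normal subjects, which implies about half get active drug first. The order is not stated for every study, and the number of women is not given. The number affected therefore cannot be calculated.

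**3. Whether the screening test covers day 1.** Screening is a separate paid visit (sections 9.d and 20). No maximum interval from screening to Test Day 1 is stated. Section 9.e also allows a call-back after the initial visit, according to COMT genotype or PPI level: "subjects may be asked to come back for further testing, if they indicate they would like to do so". The age of the screening test on day 1 is thus open-ended.

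**4. Lag to the next listed test.** After an active dose on day 1, the next listed test is on day 2. The lag equals the interval between test days, 7 to 30 days. The post-menses window restricts which lags can occur:

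- Both days in one window: at most 10 − 1 = 9 days apart, so the lag is 7 to 9 days.
- Any lag of 10 days or more needs a new menses before day 2.
- Assuming a 28-day cycle, the shortest lag across two windows is 28 + (1 − 10) = 19 days and the longest is 28 + (10 − 1) = 37, cut to 30 by the schedule. On that assumption, lags of 10 to 18 days do not occur.

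The window thus reduces the possible lags to 7–9 or 19–30 days. In every case the test follows the exposure.

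**5. Whether other text supplies a day-1 test.** Section 9.d says: "If subjects fail screening criteria for recreational drug use prior to any TEST SESSION day, they will not be tested further". That concerns recreational drugs. Section 11 gives toxicology as the purpose of the urine taken from controls at testing. Section 15 says the toxicology urine also serves for pregnancy testing, but places that screen beside the EKG and psychological battery, straight after the pre-acceptance history and physical, so it reads as part of the screening work-up. None of these states a pregnancy test on Test Day 1.

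**6. Day numbering.** Section 9.d mentions a second and a third test day, so the day 2 of section 11 might once have counted screening as day 1. The listed tests would then be at screening and the first dosing day, leaving the second dosing day uncovered. The count in step 1 is again 1 of 2. Section 9.g labels the first dosing day Test Day 1, which favours the plain reading.

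**The case against.** The strongest reply is that a day-1 test is implied. The toxicology urine is also used for pregnancy testing (section 15), a drug-use screen applies before any test session (section 9.d), and urine is taken on day 1 before the dose (section 9.g). The schedule is only a model example and does not even mention toxicology, so the absence of a dip-stick line there shows little. This is a fair account of what may have been intended. It does not displace section 11, the one place where occasions are named, and a reader should not have to combine three sections to find a test that section 11 leaves out.

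The second reply is that pregnancy on day 1 is already unlikely. A woman dosed within 10 days after menses has recently menstruated, however long ago she was screened. At lags of 10 days or more, a woman who was pregnant on day 1 and did not menstruate would not qualify for day 2. Section 10 excludes pregnancy in controls and patients, and section 14 requires contraception and self-report. Section 11 also repeats the screening of controls at testing.

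Most of this stands and keeps the point minor. Three limits remain. The repeat screening is stated for controls, with no equivalent for women with schizophrenia. No check of the menstrual window is described, and the blood drawn is only stored for possible later hormone analysis. The protocol also judged a day-2 test worthwhile under the same contraception and window.

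**Conclusion.** The concern holds as a modest safety gap. Under the stated rule, 1 of 2 dosing days has no listed pregnancy test, and either day can be the active one. For a woman given active drug on day 1, the next listed test comes 7 to 30 days after exposure.

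This rests on taking section 11 as the governing text and on the day numbering of section 9.g; the alternative numbering moves the gap to the other dosing day. The residual risk is probably low, and the documents do not allow it to be estimated. Nothing here shows that a test was omitted in practice or that anyone was harmed. The SAP already reports memantine results, so the correction matters for any continuing or future dosing of women under this protocol. Sample size, power and type I error do not change.

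**What to change.** In section 11, state that women have a urine pregnancy test at initial screening and before dosing on each test day, with a positive result excluding them. In the section 9.g schedule, add the pregnancy test for women to the 0815–0845 urine collection on both days, with the result read before the 0900 dose. That collection ends 15 minutes before dosing begins (0900 − 0845).

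The cost is one changed phrase in section 11, one added line per test day in section 9.g, and at most one extra dip-stick per woman, on urine already collected. If a day-1 test is already routine, only the wording changes.

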12. INFORMED CONSENT

Recruitment of subjects and informed consent procedures will follow [name] established methods. For all subjects we will have a consent form indicating any or all of the following procedures to be used: startle gating, mismatch negativity, gamma band synchronization, MCCB, negative priming and latent inhibition. Subjects included in drug studies will be told of any potential side effects they may expect from the drug to be used during testing. Specifically, all subjects will be asked to read a description of the test drug, modified from the Physician's Desk Reference, which includes the following information: 1) the typical indications for this drug; 2) the recommended starting dose for this drug, and details regarding typical maintenance doses and schedules; 3) common side effects experienced by individuals taking this drug, based on trials with the indicated clinical population; and 4) an assessment of the likelihood that they will experience significant side effects from this drug, in the doses to be used in this study. In all cases, fully informed consent will be obtained and [name] will be directly available to clarify any questions raised by a subject. Signed and witnessed consents will be kept on file with other patient data. The UCSD IRB has authorized no waivers or modifications of normal procedures.

Subjects will be carefully screened to ensure their ability to comprehend study procedures, risks, and benefits. Potential participants will be fully informed of all risks and benefits prior to giving their written informed consent and prior to enrollment in the study. Participants will be asked to repeat back understanding of this material, and if there is any question as to whether a person is able to provide informed consent then they will not be permitted to participate. A copy of the signed consent form will be stored in a separate locked filing cabinet from other de-identified coded materials, and a copy will be given to the study participant.

All study personnel involved in obtaining written informed consent will have completed a web-based course with post-test on Human Subject Research Protections and Good Clinical Practice, in addition to being trained by the Principal Investigator (PI) on obtaining informed consent. These study personnel will also be authorized to obtain informed consent by the IRB and Human Studies Subcommittee. Informed consent will be documented using standardized IRB-approved forms. The forms will be presented to all potential participants at the initial visit. Briefly, the informed consent form will describe the purpose of the study, procedures and participant involvement, nature of assessments and treatments, potential risks, alternatives to participation, costs and compensation, confidentiality, right to withdraw, potential benefits, relevant contact personnel, and information regarding the Health Insurance Portability and Accountability Act (HIPAA) of 1996. Because participation in the proposed study is entirely voluntary, patients can choose to discontinue the study at any point for any reason and this will in no way affect future medical treatment decisions or practices.

Genetic Testing, Material & Storage: One goal of this proposal is to identify single nucleotide polymorphisms associated with differential sensitivity to drug effects on sensorimotor gating and neurocognition in clinically normal and schizophrenia subjects. To accomplish this, blood samples will be sought from all subjects by venopuncture at the UCSD Medical Center. Five ml (less than half of a tablespoon) of blood will be collected. DNA will be extracted by the Genomics Core Laboratory at UCSD. Tubes will be stored in a -80 degree freezer located at the CTF room A-310. All samples will be identified only by their subject ID to ensure confidentiality.

Subjects will be fully informed of the risks involved in providing a sample for DNA testing. Subjects will be told that [name] will be responsible for how the blood specimen is used and that the specimens collected from the subjects and the DNA that they contain may also be used in additional research by [name]. However, neither the blood, DNA nor information that identifies the subject will be shared with any other entity or collaborator or other party outside of our immediate research lab at UCSD. It will not be shared with any member of their family. Subjects will also be told that none of the results of their genetic tests could provide meaningful information related to their likelihood of developing or transmitting any specific disorder or medical condition. Results of the research that are specific to the subject will not be shared with anyone whether they have authorized it or not. If any publication results, the subject's name will not be used.

13. ALTERNATIVES TO STUDY PARTICIPATION

As stated in the current consent form, the alternative to study participation is to withdraw from the study.

14. POTENTIAL RISKS

Potential risks are minimal. The rating scales and questionnaires are innocuous. Startle testing exposes subjects to the application of skin tape electrodes and to brief loud sounds, which in >30 years of testing in the [name] and [name] laboratories has caused no side effects. All other measures require only computer keyboard use and involve no risk. The cumulative risks of this proposal are judged as small. Below is a summary of the language in the consents.

1. An alcohol swab is used to clean the skin before electrodes are applied and some minor skin irritation and redness may occur.
2. Some participants might experience fatigue, boredom or irritation during the test session.
3. Some participants may be embarrassed or feel uncomfortable by some of the questions asked in the questionnaires.
4. Eyeblink startle exposes subjects to the application of skin tape electrodes and to brief loud sounds, which in our experience has caused no side effects.
5. During the study, your blood pressure and pulse will be regularly monitored.
6. Blood drawing may cause a small amount of pain. In addition, a temporary bruise or "black and blue mark" may develop. Rarely, people faint after having their blood drawn. Very rarely, the vein in which the needle has been inserted may become inflamed or infected, which can be treated.

For the drug evaluation study, the proposed drugs carry a very small risk of toxicity or adverse side effects in the doses to be used in this study. The most common side effects associated with each drug are listed in Section 8 above, and typically include nausea, somnolence and dizziness. We do not plan to administer these drugs to subjects in whom it is contraindicated, such as subjects with known cardiovascular or neurological disorders. The doses selected for use in these studies are in the low- or below-therapeutic range for these drugs when they are used clinically, and in most cases, the selected dose is equal to or less than the lowest recommended starting clinical dose for the drug. To address the potential for some of these drugs to produce changes in blood pressure, we will carefully monitor subjects' vital signs, and will not release subjects from the hospital until their vital signs are within normal limits. To address the possible side effect of somnolence, we will instruct subjects to arrange for their transportation from the hospital on test days. For studies that include women of childbearing potential, there is the possibility of unforeseen harm to an unborn child due to the administration of drugs. To address this risk, all female subjects will be asked to provide a urine sample to test for pregnancy and we will exclude participants who test positive. Additionally, all female subjects in these studies will be required to use a non-drug birth control method, such as abstinence, diaphragm, non-hormone intrauterine device to prevent pregnancy during the study. Subjects will be told to report if their menstrual cycle is inconsistent or if suspect that they are pregnant. Drugs will be dispensed by a licensed physician, and a licensed physician will be present on the premises at all times during testing. The consent forms include the related risks specific to the drug it refers to.

